12.3	Protocol Deviations.....	46
12.3.1	Definitions.....	46
12.3.2	Procedures for Reporting Protocol Violations.....	47
12.4	Publication and Data Sharing Policy.....	48
12.4.1	Use of Study Findings	48
12.4.2	Publication.....	48
13	STUDY ADMINISTRATION	49
13.1	Study Leadership.....	49
14	CONFLICT OF INTEREST POLICY.....	50
15	LITERATURE REFERENCES.....	51
16	VERSION HISTORY	53

LIST OF ABBREVIATIONS

Abbreviation	Definition
AE	Adverse event
ACE	Angiotensin Converting Enzyme
ARB	Angiotensin Receptor Blocker
CBC	Complete Blood Count
CLIA	Clinical Laboratory Improvement Amendments
COVID-19	Coronavirus Disease 2019
CRF	Case Report Form
DSMB	Data Safety Monitoring Board
FDA	Food and Drug Administration
GCP	Good Clinical Practice
GLP	Good Laboratory Practice
HICFA	Hawaii Center for AIDS
HIPAA	Health Insurance Portability and Accountability Act
IATA	International Air Transportation Association
ICF	Informed Consent Form
ICH	International Council for Harmonization of Technical Requirements for Registration of Pharmaceuticals for Human Use
IRB	Institutional Review Board
NP	Naso-Pharyngeal
NSAID	Non-steroidal Anti-inflammatory Drug
OHRP	Office for Human Research Protections
OP	Oro-Pharyngeal
PBMC	Peripheral blood mononuclear cell(s)
PD-1	Programmed death receptor-1
PI	Principal Investigator
PID	Patient identifier number
QA	Quality Assurance
QC	Quality Control
qd	Daily
SAE	Serious Adverse Event
SID	Subject identifier number
SOP	Standard Operating Procedures
Sub-I	Sub-Investigator(s)
UP	Unanticipated Problem
US	United States
WBC	White Blood Cell count
WHO	World Health Organization

STATEMENT OF COMPLIANCE

The trial will be carried out in accordance with International Conference on Harmonization Good Clinical Practice (ICH GCP) and the following:

- United States (US) Code of Federal Regulations (CFR) applicable to clinical studies (45 CFR Part 46, 21 CFR Part 50, 21 CFR Part 56, 21 CFR Part 312, and/or 21 CFR Part 812)

The principal investigator, co-investigators and clinical trial site staff who are responsible for the conduct, management, or oversight of this clinical trial have completed Human Subjects Protection and ICH GCP Training.

The protocol, informed consent form(s), recruitment materials, and all participant materials will be submitted to the Institutional Review Board (IRB) for review and approval. Approval of both the protocol and the consent form must be obtained before any participant is enrolled. Any amendment to the protocol will require review and approval by the IRB before the changes are implemented to the study. In addition, all changes to the consent form will be IRB-approved; a determination will be made regarding whether a new consent needs to be obtained from participants who provided consent, using a previously approved consent form.

Principal Investigator: [name] MD

Signed:

Date:

[figure not shown]
PROTOCOL SUMMARY

Title:	Randomized, Double-Blind, Placebo-Controlled Pilot Clinical Trial of the Safety and Efficacy of Telmisartan for the Mitigation of Pulmonary and Cardiac Complications in COVID-19 Patients
Study Description:	This study will enroll 40 symptomatic outpatients tested positive for COVID-19. Participants to be randomized 1:1 to Telmisartan (40 mg) vs placebo to be administered orally once daily x 21 days. Daily, the study participants will be asked to keep a record of the severity of their fever, dyspnea, and fatigue and to take their blood pressure (BP) and temperature. Study visits will occur on day 1 (entry), day 4, day 10 and day 21. Oro-pharyngeal swabs, and approximately 25 cc of blood will be collected at each study visit for safety labs and for the evaluation of the renin-angiotensin system (RAS) system and for various blood biomarkers of organ function/coagulation, inflammation, leukocyte chemotaxis, tissue remodeling/fibrosis and immune exhaustion.
Objectives:	
Primary Objective: Compare the maximum clinical severity of disease between the telmisartan and the placebo arms utilizing a modified WHO COVID-19 7-point ordinal scale
 
Hypothesis: Overall severity of disease will be less on the telmisartan arm compared to the placebo arm
 
Secondary Objectives:
 
▪ Evaluate the safety and tolerability of Telmisartan when given over 21 days to patients with COVID-19 disease▪ Compare the circulating RAS metabolites between the 2 arms; assess the ability of RAS metabolites to predict clinical status▪ Compare plasma biomarkers between the 2 arms; assess the ability of plasma biomarkers to predict clinical status 
Exploratory Objective:
 
▪ Longitudinally assess the detectability of SARS-CoV-2 virus
Endpoints:	
Primary Endpoint: Maximal clinical severity of disease utilizing a modified WHO 7-point ordinal scale
 
Secondary Endpoints:
 
▪ Number of grade II or higher adverse events (AE) through day 21 of study▪ Levels of various components of the RAS system including Ang(1-12), AngI, AngII and Ang(1-7)▪ Levels of various blood biomarkers
Study Population:	Forty (40) symptomatic participants diagnosed positive for COVID-19.

H051: v.3 (rev: 3/25/21; 8/13/20; 6.1.2020; 4/27/2020)

Phase:	Phase II trial
Description of Sites/Facilities Enrolling	Single site study at the John A. Burns School of Medicine – Kakaako campus, University of Hawaii
Description of Study Intervention:	Telmisartan is a member of a family of angiotensin receptor blockers (ARB) anti-hypertensive medications.
Study Duration:	One year total duration of study
Participant Duration:	21 day participation for each patient

SCHEMATIC OF STUDY DESIGN

2 INTRODUCTION: BACKGROUND INFORMATION AND SCIENTIFIC RATIONALE

2.1 BACKGROUND INFORMATION

COVID-19 Pandemic As of the writing of this protocol, there 2,394,278 cases of Covid-19 in 185 countries and regions throughout the world and approximately 83,764 new cases occur daily. In the largest cohort of >44,000 persons with COVID-19 from China, while disease severity was mild to moderate in 81%, pulmonary and multi-organ system dysfunction complications account for the majority of the morbidity and mortality of this disease. Severe disease (dyspnea, hypoxia, or >50% lung involvement on imaging) occurred in 14%, and critical disease (respiratory failure, shock, or multiorgan system dysfunction) occurred in 5%. Among U.S. COVID-19 cases with known disposition, the proportion of persons who were hospitalized was 19%¹. Among patients who developed severe disease, the median time to dyspnea ranged from 5 to 8 days, the median time to acute respiratory distress syndrome (ARDS) ranged from 8 to 12 days, and the median time to ICU admission ranged from 10 to 12 days²⁻⁵. Age is a strong risk factor for severe illness, complication and death¹, and the case fatality is higher for patients with co-morbidities: 10.5% for those with cardiovascular disease, 7.3% for diabetes, and approximately 6% each for chronic respiratory disease, hypertension and cancer⁶.

Figure 1. ‘Deleterious’ and ‘Protective’ Aspects of the Renin-Angiotensin System (RAS)

Compared to other states, Hawaii has had relatively few cases (574 confirmed COVID-19 cases as of April 19, 2020). Early institution of public health measures including the mandatory 14-day quarantine for all individuals flying into Hawaii have been credited for these low number. However, without an effective vaccine, as normalization of the economy and re-opening of our state to visitors are attempted, more cases of COVID-19 may be inevitable.

Renin-Angiotensin System (RAS) RAS is a hormonal system best known for its ability to regulate blood pressure, fluid and electrolyte balance and systemic vascular resistance. As shown in very simplistic form in Figure 1, angiotensinogen, released by the liver, is converted by the action of renin into angiotensin I [AngI; also known as Ang-(1–10)]. AngI is subsequently converted to angiotensin II [AngII; Ang-(1–8)] by the angiotensin-converting enzyme (ACE1) found on the surface of vascular

endothelial cells, predominantly in the lung.

The effect of AngII is receptor-specific with 2 predominant receptors: angiotensin II type 1 receptor (AT1R) and angiotensin II type 2 receptor (AT2R). AngII/ AT1R binding leads to the classic ‘deleterious’

effects of AngII, including hypertension, arterial wall thickening, impaired lung function and fibrosis. It has increasingly been demonstrated that AngII/AT1R binding also plays an important role in lung inflammation, impaired function and fibrosis. In mouse models of ARDS, AngII/AT1R binding leads to impaired lung function and fibrosis⁷. Elevated circulating AngII concentrations in influenza A (H7N9) pneumonia were associated with higher mortality rates⁸. Angiotensin receptor blockers (ARB) medications such as telmisartan used for the treatment of hypertension and cardiovascular risk reduction exerts its known anti-hypertensive, cardio-protective effect by blocking the binding of AngII to AT1R. There is evidence that ARB may also have lung-protective effects⁹.

Accumulating evidence suggests that, in contrast, an alternative, counter-regulatory 'protective' arm of the RAS system exists and that it is mediated by 2 alternative pathways as shown in Figure 1 which may be inter-related: (1) an alternative interaction of angiotensin II with AT2R; and (2) the activity of the enzyme angiotensin-converting enzyme 2 (ACE2) to cleave AngI and AngII ultimately to angiotensin (1-7) [Ang(1-7)]. Both the angiotensin II/AT2R and the angiotensin (1-7) /Mas receptor (MasR) interactions promote the counter-regulatory 'protective' effects of RAS that includes vasodilation, anti-inflammatory and anti-fibrotic responses. Our collaborator for this project ([name] PharmD) and his colleagues have published that increased activity of this counter-regulatory RAS system as measured circulating angiotensin peptide levels correlate with survival of Acute Respiratory Distress Syndrome (ARDS) patients¹⁰.

SARS-CoV2 and ACE2 Severe Respiratory Syndrome Coronavirus 1 (SARS-CoV-1) responsible for the SARS epidemic in 2002 to 2004, and the SARS-CoV-2 virus responsible for the current COVID-19 pandemic, both utilize ACE2 as the receptor to enter the cells it infects^{11,12}. ACE2 is found attached to the cell membrane of lung alveolar epithelial cells, enterocytes of the small intestines, arterial and venous endothelial cells and arterial smooth muscle cells in most organs¹³. **It has been postulated that the lack of ACE2 may lead to unopposed AngII accumulation and local unfavorable RAS activation, and therefore may be responsible for much of the organ injury in COVID-19 disease¹⁴.** Several data support this view. Down-regulation of ACE2 abundance on cell surfaces has been demonstrated in mouse studies after the initial engagement of SARS-CoV-2 spike protein¹⁵. Down-regulation of ACE2 activity in the lung in response to bacterial endotoxin in a murine model has been shown to promote the release of proinflammatory chemokines, increase neutrophil infiltration, and exaggerate lung injury¹⁶. Elevated levels of plasma AngII have been demonstrated in a small study of patients with COVID-19 which in turn correlated with total viral load and degree of lung injury¹⁷. In autopsies of patients who died from SARS, 35% of heart samples showed the presence of viral RNA, which in turn was associated with reduced ACE2 protein expression¹⁸.

Telmisartan an ARB approved in 1998 for the treatment of hypertension and for cardiovascular risk reduction. It is marketed by Boehringer Ingelheim Pharmaceuticals, Inc as Micardis but is also available in generic form. The dosage of 40 mg once daily is the recommended starting dose. The drug has been evaluated for safety in more than 3700 patients in clinical trials. Adverse events are generally mild with overall rates similar to that in placebo and rarely require discontinuation of therapy. The adverse events most commonly seen were upper respiratory infection, back pain, sinusitis, diarrhea and pharyngitis. There are only a few contraindications to its use in the package insert. It is contraindicated in individuals with diabetes who are also receiving concomitant aliskiren, has a black box warning to discontinue telmisartan when pregnancy is detected because of fetal toxicity and should not be used while breast feeding. Telmisartan may also increase digoxin and lithium levels upon co-administration. Nonsteroidal

anti-inflammatory agents and COX2 inhibitors could reduce the antihypertensive effects of telmisartan and can decrease renal function. **Evidence for potential antiviral activity of Telmisartan** Computational methods for screening and identifying candidate therapeutic compounds are a reliable and productive approach in drug discovery. Our group implemented a structure based virtual screening method to identify compounds that may have activity against SARS-CoV-2. Of the over 1900 compounds screened, we identify an angiotensin receptor blocker with binding affinity for the viral 3 Chymotrypsin-like protease (3CLPro) ([name], unpublished data. comparable to the N3 inhibitor of the crystal structure (PDB 6LU7). Its lowest energy conformer places the benzoic acid moiety of telmisartan over the active site of 3CLpro defined by Cys 145 and His 41¹⁹. By amino acid sequence alignment of SARS CoV pp1ab with SARS-CoV-2 pp1ab, 3CLpro is thought to be responsible for cleaving the SARS-CoV-2 pp1ab at 11 sites that result in the formation of 11 non-structural proteins (Nsp)²⁰. Among these proteins are Nsp12, the RNA dependent RNA polymerase (RdRp), a key enzyme responsible for replication of SARS-CoV-2 RNA, Nsp7 and Nsp8 (cofactors for RdRp) and Nsp 13 (Helicase).

[figure not shown]
We further characterized the interaction between telmisartan and 3CLpro using an atomistic molecular dynamics simulation. The N3 ligand associated with the crystal structure was used to locate the substrate binding cleft of 3CLpro and study the interaction with telmisartan. One monomer (the 3CL protease exists as a dimer, but the binding site is far from the monomer-monomer interaction area and one telmisartan molecule were solvated in water and were allowed to interact in unbiased simulations over a timeframe of microseconds. Preliminary data suggest that telmisartan forms a favored interaction with the 3CLpro binding site. It is important to note that further inside from the initial binding site, there is a hollow area that includes hydrophilic residues, making further tight binding possible. Our results support the bioinformatics study which suggests telmisartan shows a promising binding propensity for 3CLpro.

RATIONAL FOR THE STUDY:

There is a need for a therapeutic modality to minimize the severity of COVID-19 disease Currently there are no FDA-approved drugs demonstrated safety and efficacy in randomized controlled trials in patients with COVID-19. As of April 10, 2020, there were over 440 clinical trials of COVID-19 registered on ClinicalTrials.gov. While there were a few trials proposing to utilize another ARB losartan singly or in combination, to the best of our knowledge this is the only trial to propose telmisartan.

Telmisartan is an FDA-approved drug. **Repurposing FDA approved drugs can expedite the treatment of diseases particularly for conditions of unmet needs.** The safety of these drugs has already been evaluated by the FDA and the risk associated with their use is well documented. Repurposed drugs can lower development costs and shorten the time it takes to treat patients.

Figure 2. (Left) Unopposed SARS-CoV2 viral influence on the RAS and (Right) SARS-CoV2 viral influence on RAS with the addition of Telmisartan (Adapted from Stone, RE et al Journal of Neuroimmune Pharmacology 2019)

Our central hypothesis is that the use of telmisartan will mitigate the symptomatic severity of COVID-19 disease by influencing the balance between the pathologic and counter-regulatory aspects of RAS. As shown in Figure 2A (left), the binding of the SARS-CoV2 virus to ACE2 results in an imbalance in the

RAS with an increase in the pathologic effects mediated by a decrease in ACE2, i.e. an increase in AngII with excessive binding to AT1R and a decrease in the counter-regulatory protective effects of angII/AT2R and A(1-7)/MasR binding. *We hypothesize that telmisartan (Figure 2 right) will block the AT1R receptor, and correct this imbalance, i.e. resulting in a decrease in AngII/AT1R binding and an increase in AngII/AT2R and A(1-7)/MasR binding.*

In addition, *we hypothesize that telmisartan may have an anti-viral effect against SARS-CoV-2*. By computer simulation, telmisartan appears to have the ability to bind to the 3CL protease and may effectively prevent the creation of discrete viral proteins necessary for the development of infectious SARS-CoV-2 virions.

This pilot study will provide **important preliminary data on the pathogenesis of COVID-19 disease**. We propose assays of RAS peptides performed by a laboratory with demonstrated expertise in this area. Assays of circulating angiotensin peptides levels conducted in Dr. [name]'s laboratory have been used to correlated clinical outcomes in patients with Acute Respiratory Distress Syndrome¹⁰. We also propose to assay various plasma biomarkers of organ function/coagulation, inflammation, leukocyte chemotaxis, tissue remodeling/fibrosis and immune exhaustion.

2.2 POTENTIAL RISKS AND BENEFITS

2.2.1 KNOWN POTENTIAL RISKS

According to the FDA- approved package insert, telmisartan is contraindicated in individuals with a history of known hypersensitivity to the drug or its components and in individuals with diabetes who are also receiving concomitant aliskiren. It is not recommended in pregnant or breast feeding female because it can reduce fetal renal function and increase fetal and neonatal morbidity and death. NSAIDs is believed to increase risk of renal impairment and loss of anti-hypertensive effect. Co-administration with digoxin increases the digoxin peak plasma concentration (49%) and in trough concentrations (20%). Reversible increases in serum lithium concentrations and toxicity have been reported during concomitant administration of lithium.

The drug has been evaluated for safety in more than 3700 subjects in clinical trials, including 1900 for over 6 months and more than 1300 for over one year. Adverse experiences have generally been mild and transient in nature and have infrequently required discontinuation of therapy. In placebo-controlled trials, the overall incidence of adverse events was similar to that in patients treated with placebo. Adverse events occurring at an incidence of $\geq 1\%$ in patients treated with telmisartan and at a greater rate than in patients treated with placebo, irrespective of their causal association, were as below:

	Telmisartan n=1455 %	Placebo n=380 %
Upper respiratory tract infection	7	6
Back pain	3	1
Sinusitis	3	2
Diarrhea	3	2
Pharyngitis	1	0

The incidence of adverse events was not dose-related and did not correlate with gender, age, or race of patients. Warning and precautionary measures recommended in the package insert include the need to correct or follow closely patients who are volume- or salt-depleted; and to monitor for risk of hyperkalemia particularly in those with advanced renal impairment, heart failure or on renal replacement therapy.

2.2.2 KNOWN POTENTIAL BENEFITS

Telmisartan is indicated for the treatment of hypertension, to lower blood pressure. Lowering blood pressure reduces the risk of fatal and nonfatal cardiovascular events, primarily strokes and myocardial infarctions. According to the package insert, the antihypertensive effects of Telmisartan have been demonstrated in six principal placebo-controlled clinical trials, studying a range of 20 to 160 mg; one of these examined the antihypertensive effects of Telmisartan and hydrochlorothiazide in combination. The studies involved a total of 1773 patients with mild to moderate hypertension (diastolic blood pressure of 95 to 114 mmHg), 1031 of whom were treated with Telmisartan. Following once daily administration of Telmisartan, the magnitude of blood pressure reduction from baseline after placebo subtraction was approximately (SBP/DBP) 6 to 8/6 mmHg for 20 mg, 9 to 13/6 to 8 mmHg for 40 mg, and 12 to 13/7 to 8 mmHg for 80 mg. Larger doses (up to 160 mg) did not appear to cause a further decrease in blood pressure.

Some beneficial effects not related to its anti-hypertensive effects have also been reported at least for ARB medications in general. ARB medications have been reported to suppress mediators of inflammation, including ROS and C-reactive protein, and they increase expression of inhibitory κ B (an inhibitor of nuclear factor- κ B)^{21,22}. It has also been reported that the use of ARBs lower progression of emphysema and lower incidence of inflammatory complications including rates of pneumonia and influenza⁹. In animal models, inhibition of AT₁ signaling has been shown to attenuate experimental pulmonary fibrosis induced by bleomycin, radiation, and hyperoxia. In a pilot clinical study, Couluris et al. evaluated the effect losartan, an AT₁ antagonist, on idiopathic pulmonary fibrosis progression over 12 months²³. The study demonstrated stable or improved pulmonary function testing in 12 of the 17 patients treated with losartan. The authors concluded that losartan is a promising low-toxicity agent for treatment of idiopathic pulmonary fibrosis that requires more extensive evaluation in a placebo-controlled multicenter trial.

3 OBJECTIVES AND PURPOSE

Primary Objective: Compare the maximum clinical severity of disease between the telmisartan and the placebo arms utilizing a modified WHO COVID-19 7-point ordinal scale

Secondary Objectives:

- Evaluate the safety and tolerability of Telmisartan when given over 21 days to participants with COVID-19 disease

- Compare the circulating RAS metabolites between the 2 arms; assess the ability of RAS metabolites to predict clinical status

- Compare plasma biomarkers between the 2 arms; assess the ability of plasma biomarkers to predict clinical status

Exploratory Objective:

- Longitudinally assess the detectability of SARS-CoV-2 virus

4 STUDY DESIGN AND ENDPOINTS

4.1 DESCRIPTION OF THE STUDY DESIGN

A 21 day, randomized, double-blind, placebo-controlled pilot study of Telmisartan in patients with symptomatic COVID-19 disease. The study is structured as a pilot study to assess whether telmisartan may be effective in mitigating the pulmonary and cardiac complications of COVID-19 disease. Forty study participants will be randomized 1:1 to receive Telmisartan 40 mg or Placebo once daily for 21 days. Study specific procedures include daily log of fever, dyspnea and fatigue symptomology and daily blood pressure and temperature monitoring to be performed by the participant. Oro-pharyngeal swab, and blood draw for safety labs and research assays will be obtained at day 1 (entry), day 4 (72 hours post entry), day 10 and day 21 (end of study).

4.1.1 PRIMARY ENDPOINT

The primary endpoint is the maximum clinical severity of disease for each participant as assessed on a 7-point **Clinical Status** ordinal scale adapted from the WHO MASTER PROTOCOL for the Treatment of COVID-19 in Hospitalized Patients. The WHO 7-point scale was modified by adding sub-categories for the categories of 'Not hospitalized, limitation on activities' (based on scoring on a **Symptom Scale** to be filled out by participants daily, as explained below), as well as for the 'Hospitalized, requiring supplemental oxygen' and 'Hospitalized, on non-invasive ventilation or high flow oxygen devices' categories. For non-hospitalized participants, the maximum clinical severity recorded for any day \geq day 3 of study will be used. For participants who become hospitalized, the maximum clinical severity prior to discharge will be used.

Clinical Status Classification	Score
Not hospitalized, no limitations on activities	1.0
Not hospitalized, limitation on activities as assessed by the Symptom Scale below	
(a) \leq 3 points	2.0
(b) 4-6 points	2.25
(c) 7-9 points	2.5
(d) 10-12 points	2.75
Hospitalized, not requiring supplemental oxygen;	3.0
Hospitalized, requiring supplemental oxygen:	
(a) Requiring supplemental oxygen at < 6 L/min	4.0
(b) Requiring supplemental oxygen at ≥ 6 L/min	4.5
Hospitalized, on non-invasive ventilation or high flow oxygen devices	
(a) Non rebreather mask	5.0
(b) Noninvasive ventilation (NIV), high flow O ₂ devices	5.5
Hospitalized, on invasive mechanical ventilation or ECMO	6.0
Death	7.0

'**Symptom Scale**' to be used for sub-classification of the 'Not hospitalized, limitation on activities' category on the modified WHO 7-point ordinal scale is as shown below. The participant will be asked to daily grade each symptom by severity to obtain a total score. For example, the assessment of grade 2 fever (2 points), grade 1 breathing (1 point) and grade 3 fatigue (3 points) will result in a total score on the symptom scale of 6 for that day. Referring back to the **Clinical Status** classification above, the clinical status on the 7 point ordinal scale would be 'not hospitalized, limitation on activities (b) 4-6 points' for a clinical status score for the participant on that day of 2.25.

SYMPTOM SCALE For each symptom below, please circle and grade how bad the symptoms were from Grade 0 (None, 0 point) to Grade 4 (Severe, 4 points):	Grade 0 (No symptom) (0 point)	Grade 1 (Mild symptom) (1 point)	Grade 2 (Moderate symptom) (2 point)	Grade 3 (Moderately severe symptom) (3 points)	Grade 4 (Severe symptom) (4 points)
FEVER In the previous 24 hours, my highest temperature was	Less than 100.4° (=No fever)	100.4° to 101.4°	101.5° to 102.6°	102.7° to 103.9°	104° or above
BREATHING I am short of breath -	None of the time	A little of the time (only when doing things that require extra effort like cleaning the house or walking rapidly or uphill)	Some of the time (I have to stop for breath when walking at my own pace)	Most of the time (I have to stop for breath when speaking)	All the time (even at rest when doing nothing)
FATIGUE I have -	No fatigue	A little bit of fatigue but it does not prevent me from doing the things I usually do	Some fatigue which is preventing me from doing some of the things I usually do	Moderate fatigue which is preventing me from doing most of the things I usually do	Severe fatigue I cannot take care of myself (dressing, taking a shower, brushing my teeth)

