6.4.9 FOLLOW UP PHONE CALLS

Post Day 21

- Research nurse may contact the participant after the last study visit if further follow-up information on participant status is needed

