6.4.10 DISCONTINUATION OF STUDY TREATMENT

The study treatment will be prematurely discontinued for the following reasons:

- Participant becomes pregnant or starts breast-feeding
- Participant is admitted to the hospital
- Participant requires a prohibited medication

The participant will be asked to continue to be followed and attend the study visits after discontinuation of study treatment. No study procedures will be performed on the participant during hospitalization.

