7.3 TIME PERIOD AND FREQUENCY FOR EVENT ASSESSMENT AND FOLLOW-UP

The occurrence of an AE or SAE may come to the attention of study personnel during study visits and interviews of a study participant presenting for medical care. During each study visit or phone call, research nurse coordinator, PI, or Sub-I will query the participant for unsolicited and solicited AEs. All AEs including local and systemic reactions not meeting the criteria for SAEs will be captured on the appropriate CRF. Information to be collected includes event description, time of onset, clinician's assessment of severity, relationship to study product (assessed only by those with the training and authority to make a diagnosis), and time of resolution/stabilization of the event. All AEs occurring while on study must be documented appropriately regardless of relationship. All AEs will be followed to adequate resolution.

Any medical condition that is present at the time that the participant is screened will be considered as baseline and not reported as an AE. However, if the study participant's condition deteriorates at any time during the study, it will be recorded as an AE. UPs will be recorded in the CRF throughout the study.

Changes in the severity of an AE will be documented to allow an assessment of the duration of the event at each level of severity to be performed. AEs characterized as intermittent require documentation of onset and duration of each episode.

The PI or Sub-I will record all reportable events with start dates occurring any time after informed consent is obtained until 7 days for non-serious AEs and 30 days for SAEs after the last day of study participation. At each study visit, the investigator will inquire about the occurrence of AE/SAEs since the last visit. Events will be followed for outcome information until resolution or stabilization.

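### The primary score of a hospitalised participant closes at discharge, so a death after discharge but within the 21-day study is not scored 7.0

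*Combined protocol and SAP*

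**What the plan says.** Section 4.1.1 opens with the endpoint: "The primary endpoint is the maximum clinical severity of disease for each participant as assessed on a 7-point" scale. Outpatient levels run from 1.0 to 2.75, hospital levels from 3.0 to 6.0, and death is 7.0. Two scoring rules follow:

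- "For non-hospitalized participants, the maximum clinical severity recorded for any day" from day 3 onward applies to those never admitted.
- "For participants who become hospitalized, the maximum clinical severity prior to discharge will be used" applies to the rest.

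Other sections bear on what is known after an admission:

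- Protocol Summary: "21 day participation for each patient".
- 6.4.10: admission ends study treatment, but "The participant will be asked to continue to be followed and attend the study visits after discontinuation of study treatment". Also, "No study procedures will be performed on the participant during hospitalization".
- 6.4.6: a release for records in case of hospitalisation is signed at entry.
- 7.1.2 and 7.3: death and inpatient admission are serious adverse events, recorded until "30 days for SAEs after the last day of study participation".
- 6.4.9: contact after day 21 is optional: "Research nurse may contact the participant after the last study visit if further follow-up information on participant status is needed".
- 9.2: the analysis dataset runs from entry to the day 21 visit.

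Section 9.3.2 names the endpoint again without giving a window.

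**The concern.** The endpoint is meant to be the worst state each participant reaches. For anyone admitted, the second rule stops the clock at discharge, and nothing elsewhere in the protocol restarts it. Admission is itself a level of the outcome, so a post-randomisation event decides which rule applies.

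The result can contradict the endpoint's own definition. The trial team would know of a later death through continued visits, calls and serious adverse event reports, yet the written rule would keep it out of the primary score. At stake is whether the reported severity distribution is correct at its worst end, and whether a choice about such a case could be made after the event is known.

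**Working it through.** **1. The rule applied to two cases.** Both participants die at home on day 15.

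- Never admitted: the first rule applies, day 15 is after day 3, and the score is 7.0.
- Admitted without needing oxygen and discharged on day 9: the second rule applies, and the score is 3.0. After a more severe first admission it could be up to 6.0.

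The outcome and the study day are the same, but the scores differ. A death during the admission is different: it happens before any discharge and is scored 7.0.

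**2. Does another section repair it?** Sections 6.4.10 and 7.3 keep the information coming, but neither links it to the primary score. Section 9.2 describes which data are in the dataset and does not change how a score is derived. The longitudinal model in 9.3.2 uses status on days 1, 4, 10 and 21, and it is additional to the primary analysis. None of these brings a post-discharge death back into the score.

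**3. The plan's own power figure.** Inputs from 9.4 are 20 per arm, placebo probabilities 0.40, 0.40, 0.05, 0.04, 0.04, 0.04, 0.03, and an odds ratio of 5.0. Section 9.3.2 sets a one-sided test and 9.3.1 a 5% level. The telmisartan vector is printed with six values for seven categories (sum 0.99), so I applied the odds ratio to the placebo cumulative odds. This gives 0.7692, 0.1832, 0.0135, 0.0100, 0.0093, 0.0087, 0.0061.

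- Simulation of 400,000 trials with the proportional-odds score test: 80.2%.
- Whitehead formula, Φ(ln 5 × √V − 1.645) with V = (40/12)(1 − Σp̄³): 82.7%.

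The stated power of about 80% is reproduced.

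**4. How many participants the rule could touch.**

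- Placebo: P(category 3 or worse) = 0.20, and 20 × 0.20 = 4.0.
- Telmisartan: the cumulative odds of category 1 or 2 are 0.80/0.20 × 5 = 20, so P(category 3 or worse) = 1/21 = 0.0476, and 20 × 0.0476 = 0.95.
- Total 4.95, about 5 of 40. This is an upper limit, since it includes deaths in hospital, which are scored correctly.

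**5. Chance of an uncounted death.** The documents give no rate for this. Assume that a fraction f of those in categories 3 to 6 die after discharge and within the study. P(categories 3 to 6) is 0.17 on placebo and 0.0415 on telmisartan.

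P(at least one) = 1 − (1 − 0.17f)^20 × (1 − 0.0415f)^20

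| f (assumed) | Expected, placebo | Expected, telmisartan | P(at least one) |
|---|---|---|---|
| 5% | 0.17 | 0.04 | 19% |
| 10% | 0.34 | 0.08 | 35% |
| 25% | 0.85 | 0.21 | 66% |

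This treats post-discharge deaths as additional to the planned deaths. If the planned death probabilities (0.03 and 0.0061) are instead taken as all deaths, with 10% or 25% of them after discharge, the chance is lower:

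- 10%: 1 − (1 − 0.003)^20 × (1 − 0.00061)^20, about 7%.
- 25%: 1 − (1 − 0.0075)^20 × (1 − 0.0015)^20, about 17%.

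**6. Effect on power.** Scoring the deaths of step 5's table as 7.0 gives one-sided power of 80.1% to 80.3%, against 80.2% under the written rule. With f = 25% in one arm only, power is 79.7% (telmisartan only) or 80.6% (placebo only).

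**The case against.** The strongest defence is that the rule misses little and that later events are still recorded as safety data. Much of that stands. Several stronger readings are tempting, and the documents do not support them.

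- **Readmissions are lost.** A reader might infer this, but the text does not say first discharge. A readmitted participant has a later discharge, and on that reading the second stay counts. This is an ambiguity, not a demonstrated omission. It does not rescue deaths after the last discharge.
- **Any death in the trial is at risk.** A reader might take the chance of any death under 9.4 as the chance of a mis-scored one. Deaths in hospital, and deaths of participants never admitted, already score 7.0.
- **The missing day 3 start distorts hospitalised scores.** Every outpatient score (at most 2.75) lies below every hospital score (at least 3.0), so outpatient status on days 1 and 2 can never set the maximum of someone admitted. Section 5.2 excludes people who need immediate admission, so hospital status on those two days should be rare.
- **Following an admission past day 21 is an error.** Section 9.2 and the 21-day participation point to a cut at day 21, while 4.1.1 follows the stay to discharge. A cut would drop later ventilation or death in a continuing stay, which the present rule may count. This is a trade-off, not a mistake.
- **The treatment comparison is materially damaged.** Step 6 shows a power change below 1 point.

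**Conclusion.** The point holds for death after discharge. It is a stated rule that gives a wrong result, not a missing detail: a participant whose worst state within the study was death can carry a score of 3.0 to 6.0. Which discharge counts after a readmission is unclear and should be settled in the same edit.

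The size is small. At most about 5 of 40 participants come under the rule on the planning assumptions, and fewer would worsen after leaving hospital. The 19% to 66% range rests wholly on assumed post-discharge death fractions of 5% to 25%, and it falls to about 7% to 17% if such deaths are part of the planned death rates. The harm is to the correctness and interpretation of the primary endpoint, not to power.

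**What to change.** Amend 4.1.1 so that the score of a participant who is hospitalised is the worst status over all admissions and after discharge, in any setting, through day 21. Score death by day 21 from any cause and in any setting as 7.0. The sources exist already: the daily log, study visits, calls, serious adverse event reports, and hospital records under the release signed at entry.

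Before unblinding, also state whether hospital status after day 21 of a continuing admission counts in the primary score, so that 4.1.1 and 9.2 agree. Either choice is defensible. If it counts, name hospital records as the source, because contact after day 21 is optional.

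The cost is two or three sentences and the ethics board approval that 11.2 requires for any amendment. Scoring through day 21 needs no new data collection.
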